## Assessing the impact of differing levels of implementation on effect of the intervention Data from the Process Evaluation (from training participant evaluation forms, peer supporter feedback meetings, peer supporter logs of support and follow up questionnaires) will be examined to see if intervention schools can be divided into 'low' or 'high' implementation groups. This exploratory work to categorise schools into groups based on implementation will be carried out blinded to the outcome. Factors, measured as binary variables, that will be considered for this analysis will be:

## Dosage

- At least 8% teachers completed the MHFA for Schools training versus less than 8%
- At least 8% of staff completed the MHFA for adults training and went on to become a peer supporter versus less than 8%

• At least 8% of staff still acting as peer supporters by time 2 follow up versus less than 8% *Reach* 

- Whether 75% or more of teachers attended the one hour awareness training versus less than 75%
- Higher than study mean for those who select 'staff peer supporter' in response to the question 'if a work related problem was making you stressed or down who would you talk to about it at school?' in the follow up questionnaires

## Fidelity

- Whether 100% course attendees indicated that all topics were covered for one and two day courses versus less than 100%
- Whether the peer supporters set up a confidentiality policy for the service versus no policy
- Whether the peer support service was advertised in three or more ways initially versus advertised in two or fewer ways
- Whether the peer support service was re-advertised at the beginning of the 2017-2018 academic year versus not re-advertised
- Whether the peer support service has been championed by a member of the senior leadership team versus not championed

Factors relating to quality of the training were considered for inclusion – as measured by training participant feedback forms - but analysis indicated that there was not sufficient differentiation between schools for this to be useful as a high or low implementation indicator.

We will examine patterns of correlation across these different factors, to determine if one composite binary measure low/high implementer can be derived. If correlation is poor and a composite measure would not clearly differentiate high and low implementing schools, correlation among the factors within each sub-heading will be considered, to see if we can determine schools that are high/low dosage, high/low reach and/or high/low fidelity. If this is also not possible then we will conclude that the concept high / low implementers does not reflect the mixed pattern of implementation within each school and we will use qualitative analyses only to consider the impact of the different aspects of implementation (dosage, reach and fidelity) on effectiveness .

If we are able to divide the schools into high / low implementers, we will compare primary outcomes among schools receiving the intervention who are high implementers, with those who are low implementers. Adjustment will be made for both school level and individual level covariates, as in the primary analysis (see section 6.2, paragraph 1). This will be carried out only for those measures of implementation which applied to between 25 and 75% of schools in the intervention arm.

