## 6.2. Primary analysis

The tested null hypothesis is that there is no difference in level of teacher wellbeing over the period of 2 years (i.e. repeated measures analysis, no primary timepoint) in schools with peer supporters that have MHFA training and those in schools that do not have such support. The primary analysis will be carried out under the intention to treat principle, analysing participants as randomised without the imputation of missing data.

- 1. The primary analysis: Repeated measures (random effects) models will be used to examine pattern of change in primary outcome over baseline, T1 and T2, adjusted for stratification variables, sex and years of experience. This will include a random effect for individual participants, and another for school. If models fail to converge, we will use robust standard errors to account for clustering at one of the levels. This model will include every teacher who has at least one measure of the outcome (i.e. at baseline, one or two year follow up). Using a maximum likelihood estimator this analysis is robust to data which are MAR [8, 9].
- 2. Results will be presented as mean difference in the primary outcome between the trial arms over the follow up period, with associated 95% confidence interval and p- value.

Assumptions and Links for each model:

The link function for this model will be the identity function, and the different model assumptions will be checked to ensure that the model is a good fit for the data. This will include, check for normality assumptions at the different levels, making sure that homoscedasticity holds, and checking that the assumption of linearity of change holds. If these assumptions do not hold, we will investigate transformations of the data to achieve normality. If the model does not converge, we will use a simpler random effects model accounting for clustering by school only.

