## 6.3. Secondary analyses

The primary analysis (i.e. mixed effects repeated measures model including every teacher who has at least one measure of the outcome i.e. at baseline, one or two year follow up) will be repeated with a treatment by time interaction term added to the model. This will allow estimation of treatment effect at 12 and 24 month follow ups separately. Analysis of secondary outcomes will include linear, ordinal and logistic regression models dependent on the nature of the outcome variable being analysed (continuous, ordinal or binary respectively).

For secondary individual level outcomes that are measured at baseline, 12 and 24 months (e.g. PHQ-8), repeated measures models will be used, these models will include random effects for clustering by individual (due to repeated measure) and by school. All individuals with at least one observation of the outcome measure will be included in the model for that outcome measure using maximum likelihood under a Missing at Random (MAR) assumption. For each secondary individual level outcome that are measured at baseline, 12 and 24 months, 3 models will be presented:

- Model 1: Unadjusted model Repeated measures of the outcome regressed on treatment arm accounting for clustering due to repeated measures and by school (using random effects).
- Model 2: Partially adjusted model Model 1 plus adjustment for stratification variables.
- Model 3: Fully adjusted model Model 2 plus additional adjustment for covariates. For teacher based outcomes the covariates adjusted for will be sex and years of experience, for student based outcomes sex and ethnicity will be included as covariates.

For each secondary individual level outcome measured only at baseline and 24 months, 3 models will be presented:

- Model 1: Unadjusted model Outcome at 24 months regressed on treatment arm and baseline value of the outcome, accounting for clustering by school (using a random effect).
- Model 2: Partially adjusted model Model 1 plus adjustment for stratification variables.
- Model 3: Fully adjusted model Model 2 plus additional adjustment for covariates. For teacher based outcomes the covariates adjusted for will be sex and years of experience, for student based outcomes sex and ethnicity will be included as covariates.

For each secondary school level outcome measured only at baseline and 24 months, 2 models will be presented:

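### The high versus low implementation comparison in Section 6.6 has neither baseline WEMWBS as a covariate nor a group-by-time term, so a stable baseline gap left unexplained by the listed covariates passes in full into the estimate

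*SAP*

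**What the plan says.** Section 6.6 (the text after the fidelity list) says that, if intervention schools can be divided, the team will "compare primary outcomes among schools receiving the intervention who are high implementers, with those who are low implementers". On adjustment it says: "Adjustment will be made for both school level and individual level covariates, as in the primary analysis", and points to paragraph 1 of Section 6.2.

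That paragraph describes a random effects model for WEMWBS "over baseline, T1 and T2, adjusted for stratification variables, sex and years of experience". Baseline WEMWBS is therefore one of three outcome times and not a covariate. The result is a single "mean difference in the primary outcome between the trial arms over the follow up period". A term that lets the group difference vary by time appears only in Section 6.3, where the primary analysis "will be repeated with a treatment by time interaction term added to the model". The implementation paragraph does not call on it.

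Other parts of the SAP do adjust for baseline. The mechanism comparisons earlier in Section 6.6 adjust for baseline scores, and that subsection warns about confounding when it turns to mediation. The Section 6.3 models for outcomes measured only at baseline and 24 months include the baseline value. The implementation paragraph has no baseline adjustment and no caution about confounding.

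**The concern.** Between randomised arms the expected baseline difference is zero, so leaving baseline out of the covariates does not bias the contrast through a pre-existing gap. Implementation level has no such protection. Schools are classified after randomisation from process data: training uptake, attendance at the awareness session, retention of peer supporters, advertising, and championing by senior leaders. Some of these could go with how staff already felt at baseline.

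The aim of the analysis is to say whether fuller implementation gave better outcomes. Under the stated rule, two groups of schools that differed at the start and were unaffected by implementation would still show a difference, and it would be read as an implementation effect. Doing the classification blind to outcome prevents a data-driven split. It does not prevent confounding.

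**Working it through.** **Inputs from the SAP.** Section 2.7: SD 8.4, mean 50 teachers per school, coefficient of variation of cluster size 0.5, 12 schools per arm, ICC 0.01 (pilot) and 0.05 (planning), target difference 3 points. Section 6.6: an implementation measure is used only if it applies to 25 to 75% of intervention schools, which is 3 to 9 of 12.

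**Assumed inputs.** A 6 versus 6 split; a teacher-level share of variance of 0.4 to 0.6; a correlation of 0.3 to 0.5 between implementation and a school's baseline wellbeing. None of these is in the SAP.

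**Step 1: the plan's own figures.** The SAP gives no figure for this comparison, but its power statement tests the variance inputs.
- Design effect = 1 + ((0.5² + 1) × 50 − 1) × ICC. At ICC 0.05 this is 1 + 61.5 × 0.05 = 4.075.
- Effective number per arm = 600 / 4.075 = 147.
- With a two-sided 5% test (assumed) and a t distribution on 22 degrees of freedom, power is 83.4% at ICC 0.05, 97.7% at 0.02 and 68.1% at 0.08. The SAP states over 80%, 98% and 68%, so its figures reproduce.

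**Step 2: what the stated rule estimates.** Let g be a constant gap between the groups that the listed covariates do not explain, and e the true implementation effect at T1 and T2. With complete data:
- Three waves, group main effect only: (g + (g + e) + (g + e)) / 3 = g + 2e/3.
- T1 and T2 only, same covariates: g + e.
- Group-by-time contrast, mean of T1 and T2 minus baseline: (g + e) − g = e.

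The first two readings both pass on the whole of g. The first also shrinks e by a third.

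**Step 3: check in the mixed model.** Expected generalised least squares estimates were computed with random school and teacher effects, fixed time effects, 6 versus 6 schools, 50 teachers each, and ICC 0.01 to 0.05:

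| Scenario | Main effect, three waves | Group-by-time, free baseline | Baseline means held equal |
|---|---|---|---|
| g = 3, e = 0 | 3.0 | 0.0 | 0.3 to 1.2 |
| g = 0, e = 3 | 2.0 | 3.0 | 3.0 |

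Holding baseline means equal is reasonable for randomised arms. Here it leaves part of the gap in the estimate, so a repair of that kind to Section 6.2 would not serve for Section 6.6.

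**Step 4: illustrative size.** For a median split on implementation, gap = r × 2 × 0.798 × 8.4 × √ICC.
- r = 0.3, ICC 0.01: 0.3 × 1.596 × 8.4 × 0.1 = 0.40.
- r = 0.5, ICC 0.05: 0.5 × 1.596 × 8.4 × 0.2236 = 1.50.

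SE of a 6 versus 6 contrast at one wave = √[(8.4² × ICC + 8.4² × (1 − ICC)/50) × 2/6].
- ICC 0.01: √[(0.706 + 1.397)/3] = 0.84.
- ICC 0.05: √[(3.528 + 1.341)/3] = 1.27.

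The illustrative gap is thus about 0.40/0.84 = 0.5 to 1.50/1.27 = 1.2 standard errors.

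**The case against.** **The paragraph imports covariates and does not clearly import the whole model.** A reader might infer that the SAP fixes a three-wave model for this contrast. It does not say so. Where Section 6.6 wants the primary model, in the mediation text, it says so. Analysing T1 and T2 alone is a fair reading. This stands, but it does not rescue the rule, because Step 2 shows g passing through on that reading too.

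**Not every gap is carried over.** A reader might take the point to cover any baseline difference. The part explained by free school meal stratum, region, sex and experience is adjusted for. Only the remainder is at issue.

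**The size and direction are unknown.** A reader might infer that high implementers select themselves and start with happier staff. The SAP says only that the groups are formed from process data. Schools with poorer wellbeing might equally engage more, and items such as topic coverage or a confidentiality policy have no evident link to baseline wellbeing. This stands. The 0.4 to 1.5 points is an illustration, applies the full ICC without allowing for the strata, and is about the size of sampling error. The 3-point target belongs to the randomised comparison.

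**The consequence is limited.** The analysis is exploratory, falls back to qualitative work if schools cannot be separated, and has no results table in Section 8. This stands and sets the weight of the point.

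**Conclusion.** The point holds in a narrow form. For a non-randomised contrast, Section 6.6 states a rule whose covariates omit baseline WEMWBS, and it asks for no group-by-time term. A stable gap not explained by the listed covariates passes into the estimate at 100%. That share follows from the model and does not depend on the assumed correlation; it does assume that the gap is constant over time.

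This is more than missing detail. Following the sentence as written gives a confounded result, while other parts of the SAP adjust for baseline. The documents do not support any claim that such a gap exists, that it favours high implementers, or that it has a particular size. They also do not support reading this as a threat to the trial's main result: no primary or secondary conclusion rests on this comparison. It is a minor improvement, worth making because baseline WEMWBS is already collected.

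**What to change.** In Section 6.6, replace the adjustment sentence with a rule specific to this contrast:

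1. Fit the mixed model to baseline, T1 and T2 within the intervention arm, with the Section 6.2 covariates, a group-by-time term and an unconstrained baseline. The implementation effect is the average change at T1 and T2 from baseline, high minus low. Teachers without a baseline measure stay in the model.
2. Report baseline WEMWBS by implementation group.
3. Describe the result as an observational association.
4. As a sensitivity analysis, model T1 and T2 adjusted for each teacher's baseline and the school's mean baseline WEMWBS. State that this drops, or must impute, teachers without a baseline measure. The two approaches can disagree in non-randomised groups, so name the first as the main one in advance.

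Cost: one or two extra parameters. The change contrast carries the error of the baseline means, so some precision can be lost. Twelve schools leave little to spare: an intercept, region (1), free school meal level (2) and group (1) already leave 12 − 5 = 7 school-level degrees of freedom, and a school-mean baseline term takes one more. The group-by-time contrast removes only a stable gap. Groups already on different trajectories would still be confounded, which is why the wording in item 3 is needed.

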## 7. ANALYSIS OF SAFETY

School contacts and those delivering the intervention (MHFA trainers, HSCs and those trained as peer supporters) will be asked to contact the study team within 2 working days if any untoward incident or adverse event (AE) occurs to a member of staff or student i) as a direct result of taking part in the WISE study or ii) because of changes that have occurred in the school environment due to participation in WISE (e.g. heightened awareness among staff of mental health problems leading to inappropriate referrals to specialist help sources for 'normal' student behaviour ). In these cases, study specific adverse event/incident forms will be completed, recording information on the event. Members of the study teams in Bristol and Cardiff will also be required to complete a form about any incidents or AEs that they encounter during data collections. All adverse event/incident report forms will be discussed with the Principal Investigator to assess seriousness and to explore causality. All AEs deemed to be 'serious' (SAE) will be reported to the Sponsor within 24 hours. Where the SAE is suspected to be related to the intervention and unexpected, the Chair of the TSC and the FHSREC will be notified in writing within 15 days of the study team receiving the initial report. An SAE which is not deemed to be related to the research will be reported to the TSC at the next scheduled meeting.

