## 2.5. Description of interventions

Each intervention school will receive the following:

- Staff peer support service: 8 % of staff who are nominated via confidential voting of questionnaire respondents will be selected (ensuring a mixture of gender and years of experience and (non)teaching role) and will receive 2 day MHFA training. Then will act as peer supporters to other staff members.
- INSET teacher training using MHFA for schools and colleges: Another 8 % of teachers only (targeted at tutors or heads of year) who did not receive the 2 day MHFA training, will receive one day youth MHFA course. The learning will be applied during usual interactions with students.
- Mental health awareness raising session: One hour training for all teachers, during in-service training or meeting time, that will introduce the intervention and focus on the importance of mental health issues in school.

Control schools will continue with usual practice.

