#### 2.7. Sample size and justification

The primary outcome measure will be the WEMWBS scale. A change of 3 points on this scale is close to the difference in mean scores between the highest and lowest ranked schools in the pilot study. The sample size takes account of clustering; in the pilot data from 6 schools, the WEMWBS ICC (calculated using the loneway command in Stata) for teachers was 0.01 (95%Cl 0.00, 0.05) [1]. We assume a mean of 50 teachers followed up per school after allowance for 20% dropout (with a coefficient of variation of sample size of 0.5), and an SD for WEMWBS of 8.4 (based on the pilot data). Given that estimates based on pilot data can be unreliable [2], assuming an ICC of 0.05, which is greater than that seen in the pilot, -a sample size of 24 schools (12 intervention and 12 control) would achieve over 80% power. This would rise to 98% if the ICC is 0.02, and fall to 68% for an ICC of 0.08. These estimates of power are likely to be conservative given that the sample size calculation does not account for the baseline assessment of the outcome.

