#### 8.9. Safety results

Table 12. Adverse events

Adverse event Serious Adverse event Intervention Control

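### Adverse events are solicited through more routes in intervention schools than in control schools, so the by-arm counts in Table 12 are not comparable and lean towards the intervention arm

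*SAP*

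**What the plan says.** Section 7 sets out who reports: "School contacts and those delivering the intervention (MHFA trainers, HSCs and those trained as peer supporters) will be asked to contact the study team". They are asked to report an untoward incident or adverse event if either of two conditions is met. Criterion (i) is that it happened "as a direct result of taking part in the WISE study". Criterion (ii) is that it arose "because of changes that have occurred in the school environment due to participation in WISE". The one example given for (ii) is raised awareness among staff leading to inappropriate referral of students. Separately, study team members in Bristol and Cardiff "will also be required to complete a form about any incidents or AEs that they encounter during data collections". All forms are discussed with the Principal Investigator for seriousness and causality.

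Section 2.5 places the peer supporters in intervention schools, where "8 % of staff who are nominated via confidential voting of questionnaire respondents will be selected", and says that "Control schools will continue with usual practice". Section 2.8 says that schools, teachers and students cannot be blind, and that the researchers leading outcome data collection are not blind either.

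The only planned safety output is Table 12 in section 8.9, whose shell reads "Adverse event Serious Adverse event Intervention Control". It has no effect estimate, interval or p-value. Neither section separates events by reporter or criterion, or comments on whether the two arms are observed equally.

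**The concern.** A count of reported events reflects both how often events occur and how likely each is to be noticed and passed on. Here the second part differs by arm by design: intervention schools have everything control schools have, plus reporters who come with the intervention. The solicited reporters must also link an event to WISE before reporting it, and those in schools know their allocation.

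A table by arm invites comparison even without a test. If the intervention column is higher, the reader cannot tell more harm from more reporters. If the columns are similar, that is not clear reassurance either, because the arms were not observed in the same way.

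**Working it through.** The SAP gives no adverse event rate, expected count or test, so there is no stated figure to reproduce. The check has two parts.

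**Routes by arm** (sections 2.5, 2.8 and 7)

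| Route | Intervention schools | Control schools |
|---|---|---|
| School contact | yes | yes |
| Study team at data collections | yes | yes |
| Peer supporters | yes | no |
| MHFA trainers in their trial role | yes | no |
| HSCs | yes | not stated |

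HSCs are listed among those delivering the intervention, but the SAP does not say that they have no contact with control schools. Section 2.4.2 has healthy schools teams advising on school eligibility generally. They are left out of the arithmetic, as are the trainers.

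**Illustration of size**

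Inputs from section 2.7: 50 teachers followed up per school after 20% dropout, and 12 schools per arm. Input from section 2.5: 8% of staff become peer supporters.

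- Teachers per school before dropout: 50 / 0.80 = 62.5.
- Peer supporters per intervention school: 0.08 × 62.5 = 5. This is too low if non-teaching staff are counted in the 8%.
- Across the arm: 12 × 5 = 60 additional reporters, against none in control schools.

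Assumptions not in the SAP: one contact per school; each contact or peer supporter reports a given event with probability q; the study team picks it up with probability s in either arm; reports are independent; true incidence is equal.

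- Control: P = 1 − (1 − s)(1 − q)
- Intervention: P = 1 − (1 − s)(1 − q)^6, for one contact plus 5 peer supporters

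| q | s | Control | Intervention | Ratio |
|---|---|---|---|---|
| 0.1 | 0.1 | 0.190 | 0.522 | 2.75 |
| 0.1 | 0.3 | 0.370 | 0.628 | 1.70 |
| 0.1 | 0.5 | 0.550 | 0.734 | 1.34 |
| 0.3 | 0.1 | 0.370 | 0.894 | 2.42 |
| 0.3 | 0.3 | 0.510 | 0.918 | 1.80 |
| 0.3 | 0.5 | 0.650 | 0.941 | 1.45 |
| 0.5 | 0.1 | 0.550 | 0.986 | 1.79 |
| 0.5 | 0.3 | 0.650 | 0.989 | 1.52 |
| 0.5 | 0.5 | 0.750 | 0.992 | 1.32 |

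The ratio runs from about 1.3 to 2.8 and exceeds 1 in every row. Independence pushes it up: colleagues in one school tend to know of the same events, and if their reports overlapped completely with the contact's, the ratio would fall to 1. Only the direction is informative.

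The calculation applies to events equally likely in both arms, for example distress caused by a questionnaire. It does not apply to criterion (ii) events, whose true incidence is expected to differ by arm.

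**The case against.** A reader might infer that Table 12 will show excess harm even if there is none. The SAP does not support that. Events may be few or absent, reporters are asked only for events they link to WISE, and every form is reviewed for causality. What is biased is the expected count.

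A reader might also infer that criterion (ii) cannot be met in a control school, so that its contribution is pure artefact. Both halves go too far. The criterion refers to participation in WISE, and control schools participate through surveys and data collection, so such events are very unlikely there but not excluded. A true criterion (ii) event in an intervention school is a harm of the intervention, and a lower number in controls would be a real difference.

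Three further objections have force.

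- **Shared route.** The study-team route covers both arms, and the sentence describing it carries no attribution condition. Omitting it would raise the ratios to 2.0 to 4.7 for q from 0.5 down to 0.1; those figures should not be used.
- **No formal comparison.** Table 12 is descriptive, and nothing in the text claims equal observation. That limits the consequence but does not make the columns comparable.
- **Existing provision.** PHQ-8, student SDQ and student WEMWBS are already analysed by arm, and the event form is not shown, so it may already record who reported. That makes the remedy smaller, not unnecessary.

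Asking those who deliver the intervention to report is sound surveillance. The difficulty lies only in how the reports are tabulated.

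**Conclusion.** The point holds as one about ascertainment and presentation. Peer supporters and trial trainers add reporting routes in one arm only, attribution is made by unblinded people, and Table 12 shows the totals by arm without qualification. For events equally likely in both arms, the expected count is biased towards the intervention arm. The direction follows from the SAP's text, provided the extra reporters pass on at least some events that the shared routes miss. The size is not known: 1.3 to 2.8 is an illustration resting on assumed reporting probabilities, independence and one contact per school. It is not a forecast that an excess will appear. The primary and secondary effectiveness analyses are not affected.

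**What to change.** 1. Classify each event by reporting source and by criterion (i) or (ii), coding from completed event forms where possible.
2. Split Table 12. Part (a): events reported through routes operating in both arms (school contact, study team at data collections), shown by arm. Part (b): events known only from delivery-side reporters, plus all criterion (ii) events, listed descriptively with the school's arm and without a between-arm comparison. An event reported by both kinds of source stays in part (a) unless it falls under criterion (ii).
3. Add a note to section 7 and under the table that total counts are not comparable between arms, that reporters' attribution was unblinded (which the split does not remove), and that between-arm evidence on harm comes from outcomes collected the same way in both arms: PHQ-8, student SDQ and student WEMWBS.

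The cost is a coding step, a revised table shell and a short note. The between-arm count becomes smaller. Section 6.6 shows that training feedback had already been analysed when the SAP was written, so source and criterion may have to be coded retrospectively for some events. Where source cannot be recovered, say so and list the event in part (b).
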